## **8.5. Efficacy Analyses**

Efficacy analysis will be performed separately for subjects in Cohort A and subjects in Cohort B.

No hypothesis testing is planned for efficacy endpoints analyses. Nominal p values for treatment comparisons in efficacy analysis (Cohort A) will be provided as descriptive measures and should not be interpreted as conclusive evidence.

### **8.5.1. Efficacy Analysis Approaches**

For continuous efficacy endpoints, summary statistics such as means, medians, and SDs will be provided by treatment groups. Model-based LS means and confidence intervals (CIs) for within treatment estimates and between treatment differences (Cohort A) will also be provided.

Categorical efficacy endpoints will be summarized by treatment with counts and percentages of the subjects. CIs for within treatment estimate and between treatment differences (Cohort A) will also be provided.

Time to event endpoints will be summarized using the Kaplan-Meier method.

Details for efficacy analysis methodologies will be provided in the SAP.

### **8.5.2. Adjustment of Multiple Comparisons**

No hypothesis testing is planned for the study; therefore, adjustment for multiple comparisons will not be needed.

## **8.6. Safety Analyses**

Safety analysis will be performed separately for subjects in Cohort A and Cohort B, as well as pooled across Cohorts A and B.

Safety variables include incidence of AEs or TEAEs, laboratory test results, vital signs, ECG results, and PE findings. A TEAE is defined as any AE that newly appeared or worsened in severity on or after the initiation of active treatment. All safety analyses will be based on the SP. No formal statistical analysis of the safety data will be performed.

Summary tables will be provided for all AEs by treatment group. The incidence of AEs, drug-related AEs, SAEs, and AEs leading to discontinuation of the study drug will be presented by the Medical Dictionary for Regulatory Activities system organ class (SOC) and preferred term. In addition, the incidence of AEs by severity will be presented by SOC and preferred term.

The AE summary tables will include counts of subjects. Therefore, if a subject experiences more than 1 episode of a particular AE, the subject will be counted only once for that event. Similarly, if a subject has more than 1 AE within an SOC, the subject will be counted only once in that SOC.

Laboratory test variables will be summarized by treatment group and visit using descriptive statistics (number of subjects, mean, SD, minimum, maximum). Shift tables (low, normal, high) between Baseline and post-baseline timepoints will be presented by laboratory test and treatment

group. Laboratory tests with categorical results that cannot be analyzed by change from baseline or shift table analysis will not be included in these summaries but will be listed. Data obtained from laboratory tests not required by the protocol will not be summarized but will be listed.

Descriptive statistics of vital signs and ECG results at each visit will be presented by treatment groups. PE findings will be listed for each subject.

Full details will be described in the Statistical Analysis Plan (SAP.)

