Namilumab has been studied in humans in doses ranging from 0.2 mg/kg to 8 mg/kg in Study M1 1188 001 EM; at 150 mg and 300 mg doses in Study M1 1188 002 EM (PRIORA) and Study MT 203 2004 (TELLUS); at 80 mg, 150 mg, and 300 mg in Study MT 203/CPH 001; at 20 mg, 80 mg, and 150 mg in Study M1 1188 202 (NEXUS); at 20 mg, 50 mg, 80 mg, 150 mg, and 300 mg in Study M1 1188 203 (NEPTUNE); at 150 mg in Study IZN 101 (NAMASTE); and at 150 mg in an Investigator-initiated trial (CATALYST). To date, 403 subjects or healthy volunteers have been enrolled into the clinical development program for namilumab, with 332 subjects estimated to have received namilumab. In addition, 57 subjects with COVID-19 were treated with a single dose of 150 mg namilumab in an Investigator-initiated trial in the UK known as the CATALYST study (n=55) or Investigator-sponsored compassionate use study (n=2). Overall, namilumab has been well tolerated with an acceptable safety profile for further development.

Based on the known data, the potential benefits of namilumab treatment outweigh the potential risks. Preclinical and human tissue studies have suggested that GM-CSF plays a key role in the formation of granulomas, including sarcoid granulomas. Positive clinical trials of anti-GM-CSF agents in RA, giant-cell arthritis, and COVID-19 have demonstrated a key role of GM-CSF as a driver of autoimmunity and hyperinflammation. The sarcoidosis subjects in this study will have relatively severe disease and may be receiving high doses of OCS or will have failed several agents. Current treatment strategies, including long-term use of OCS are associated with significant toxicities ([Khan, 2017](#)), and other treatment options for these subjects (cytotoxic agents and anti-TNF agents) have toxicity concerns of their own ([Callejas-Rubio et al, 2018](#)). Given that no new therapy has been approved for sarcoidosis in decades, namilumab may prove to be a useful treatment for these patients with limited options.

In summary, the anticipated potential risks include the occurrence of adverse reactions i.e., decreased neutrophil count/mild neutropenia, PAP, infection, and/or hypersensitivity reactions. No AEs suggestive of PAP, severe hypersensitivity, or severe neutropenia have been reported in the namilumab clinical program to date.

The following have been delineated as important identified risks:

- AST and/or ALT elevation.

The following have been delineated as important potential risks:

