**Table 1. Identified and Potential Risks**

Risk	Source	Key Details	Actions
AST/ALT elevation	Nonclinical studies (single-dose and repeat-dose toxicity studies); clinical studies (FIH, PRIORA, NEXUS, NEPTUNE, and NAMASTE studies)	Important identified risk	Exclusion criteria; routine PV monitoring; evaluation of Individual Case Safety Reports (ICSRs); AEs, signal detection, and aggregate reports
Decreased neutrophil count/mild neutropenia	FIH study and NEXUS study	Important potential risk	Exclusion criteria; routine PV monitoring
PAP	26-week monkey toxicity study; foamy macrophages were observed	Important potential risk	Exclusion criteria; targeted/close monitoring; Investigator Guidance for early detection and management

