#### **Secondary Endpoints:**

- Other safety endpoints including:
  - Incidence and magnitude of treatment-emergent laboratory abnormalities;
  - Change from baseline in vital signs;
  - Change from baseline in ECG parameters.

- Mean change from baseline in PET maximum standardized update value (SUVmax), SUVmean, and total glycosylation;
- Cumulative arrhythmia burden and hospitalization for cardiac events;
- Mean change from baseline in left ventricular ejection fraction (LVEF) and global longitudinal strain (GLS) on transthoracic echocardiogram (TTE);
- Cumulative oral steroid use, modified glucocorticoid toxicity index (mGTI), and mean change from Baseline in glycosylated hemoglobin (HbA1C);
- Proportion of subjects requiring rescue therapy (either cohort) and proportion of subjects successfully achieving steroid taper without requiring rescue therapy (Cohort A);
- Mean change from baseline in KSQ (General and sub-domains), Fatigue Assessment Scale (FAS), and Subject Global Assessment (SGA);
- Assessments of PPK and E-R relationships for safety and efficacy if data permit.

**Note:** For endpoints defined as mean change from baseline, the primary assessment will be at Week 34.

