## 4.2. Exclusion Criteria

**An individual will not be eligible for participation in this study if any of the following exclusion criteria are met:**

1. Hospitalized for any respiratory or cardiac illness  $\leq 30$  days prior to Screening.
2. Known pulmonary hypertension requiring therapy.
3. Systemic (oral or parenteral) antibiotic or pulse OCS treatment for any indication within 42 days prior to randomization.
4. Autoimmune disease other than sarcoidosis likely to require treatment during the subject's participation in this study.
5. Symptoms and/or signs of extracardiac sarcoidosis that are likely to warrant treatment in addition to that required for the subject's cardiac disease.
6. Estimated glomerular filtration rate (eGFR)  $\leq 30 \text{ mL/min/1.73 m}^2$  (Modification of Diet in Renal Disease [MDRD] equation) or requiring renal replacement therapy.
7. Alanine aminotransferase (ALT), aspartate aminotransferase (AST), or alkaline phosphatase (ALP)  $> 2 \times$  upper limit of normal (ULN).
8. Platelet count  $< 100,000 \text{ per mm}^3$ .
9. Hemoglobin  $\leq 9.5 \text{ g/dL}$ .
10. Absolute neutrophil count  $< 1,000 \text{ per mm}^3$ .
11. Serum albumin-corrected calcium  $> 3.5 \text{ mmol/L (14 mg/dL)}$ .
12. Positive anti-GM-CSF autoantibody, or history of pulmonary alveolar proteinosis (PAP).
13. Use of any biologic immunomodulator (approved or investigational) within the 6 months prior to Screening. Allergens for hypersensitivity desensitization or vaccines are not excluded per this criterion. Treatment with immunoglobulin within 6 months prior to Screening. Treatment with any investigational immunomodulator (e.g., Neuropilin 2 [NRP2] modulator) within 6 months prior to Screening.
14. Treatment with any Janus kinase (JAK) inhibitor within 3 months prior to Screening.
15. Participation in another interventional clinical trial within 6 months prior to Screening and throughout the duration of participation in this study.

16. History of left ventricular ejection fraction (LVEF)  $\leq 30\%$  or NYHA class III or IV heart failure.
17. Fridericia corrected QT interval (QTcF)  $> 480$  msec on the 12-lead ECG at Screening; if QTcF exceeds 480 msec, the ECG should be repeated 2 more times and the average of the 3 QTcF measures should be used to determine eligibility.  
Note: If a subject has a pre-existing bundle branch block (BBB), the QTcF exclusion cutoff will be  $> 500$  msec.

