## APPENDIX 7. LIVER SAFETY SUGGESTED ACTIONS AND FOLLOW-UP ASSESSMENTS

Phase 2 liver function stopping criteria are designed to ensure subject safety and to evaluate liver event etiology.

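### The low/normal/high shift tables cannot show how many subjects per arm had worsening AST or ALT, or by how much, although this is the one important identified risk

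*Combined protocol and SAP*

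**What the plan says.** Section 8.6 plans two laboratory displays. The first is numerical: "Laboratory test variables will be summarized by treatment group and visit using descriptive statistics (number of subjects, mean, SD, minimum, maximum"). The second is categorical: "Shift tables (low, normal, high) between Baseline and post-baseline timepoints will be presented by laboratory test and treatment" group. The section plans no formal statistical analysis of safety data, so these displays are the laboratory analysis. It leaves full details to a separate SAP, whose text is not among the documents reviewed.

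Three other places bear on how well these displays serve the liver tests:

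- **Risk.** Section 1.3 introduces a list with "The following have been delineated as important identified risks", and its only entry is "AST and/or ALT elevation". In Table 1 that row alone is labelled "Important identified risk"; the other four risks are classed as potential.
- **Entry.** Exclusion criterion 7 (section 4.2) removes a subject only when ALT, AST or ALP is above 2×ULN.
- **Endpoint.** Section 2.2 lists "Incidence and magnitude of treatment-emergent laboratory abnormalities" as a secondary endpoint and defines neither the abnormality nor the scale of magnitude.

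Appendix 7 has its own liver thresholds (ALT 3× and 5×ULN, bilirubin 2×ULN) for stopping, monitoring and reporting. Section 8.6 uses none of them in a table.

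**The concern.** A three-category shift table records only the crossing of a normal limit. For liver tests the upper limit is the relevant one, and the entry rule lets some subjects start beyond it. From there the table can record improvement but not deterioration. For everyone else it records that a rise occurred but not its size.

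This bears most on the analyte the protocol treats as its established hazard. A reader of the study report would want to compare namilumab with placebo on how many subjects reached 3× or 5×ULN and where each began. The planned categorical display cannot answer that, and half of the stated endpoint, the magnitude, has no suitable categorical summary.

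**Working it through.** The plan gives no figure to reproduce, so the check is one of classification, followed by its likely scale.

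**Inputs.** Categories low, normal, high (section 8.6). Entry limit 2×ULN (section 4.2, criterion 7). ALT thresholds 3× and 5×ULN (Appendix 7). Planned size 10 namilumab and 10 placebo in Cohort A, and 10 namilumab in Cohort B (synopsis).

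**Step 1: classify.** Let x be ALT in multiples of ULN. The planned category is high if x > 1 and otherwise normal; the low side plays no part in a rise. For comparison, use bands ≤1, >1–2, >2–<3, 3–<5 and ≥5.

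| Baseline x | Post-baseline x | Planned table | ULN-multiple bands |
|---|---|---|---|
| 0.8 or 1.0 | 1.5 | normal to high | ≤1 to >1–2 |
| 0.8 or 1.0 | 2.9 | normal to high | ≤1 to >2–<3 |
| 0.8 or 1.0 | 3.0 | normal to high | ≤1 to 3–<5 |
| 0.8 or 1.0 | 5.0 or 8.0 | normal to high | ≤1 to ≥5 |
| 1.2, 1.5 or 2.0 | 2.9 | high to high | >1–2 to >2–<3 |
| 1.2, 1.5 or 2.0 | 3.0 | high to high | >1–2 to 3–<5 |
| 1.2, 1.5 or 2.0 | 5.0 or 8.0 | high to high | >1–2 to ≥5 |

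The three raised baselines and four higher values make 3 × 4 = 12 combinations. All 12 land in the cell that also holds no change. In the banded table all 12 show as shifts.

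**Step 2: what the numerical summary adds.** Suppose one subject goes from 1.8× to 6×ULN and nobody else changes. The mean moves by (6 − 1.8)/10 = 0.42×ULN in an arm of 10, and by (6 − 1.8)/20 = 0.21×ULN across the 20 planned namilumab subjects. The maximum at that visit would read 6×ULN. It would read the same if several subjects had passed 3× or 5×ULN, and it does not show the baseline of the subject who produced it.

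**Step 3: how many subjects could start high.** The documents do not say, so the share p above ULN at Baseline is an assumption. The expected number is 30p, and the chance of at least one is 1 − (1 − p)^30, taking subjects as independent.

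| Assumed p | Expected of 30 | Chance of at least one |
|---|---|---|
| 5% | 1.5 | 0.79 |
| 10% | 3 | 0.96 |
| 20% | 6 | >0.99 |
| 30% | 9 | >0.99 |

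The loss of size for subjects starting at or below ULN does not depend on p.

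**Step 4: unscheduled values.** Chemistry is drawn at every treatment-period clinic visit (Appendix 1), so a worst value at a scheduled visit falls within the by-visit range. Appendix 7 also calls for repeat tests within 24 to 72 hours or sooner, then weekly or twice weekly, which fall between visits. Section 8.6 does not say whether those results enter a by-visit table.

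**The case against.** A reader might infer that a liver signal could be missed, and that one missed case at 5×ULN or more would be 1/10 = 10% of an arm. The documents do not support that. The by-visit maximum would print a large rise seen at a scheduled visit. Appendix 7 lists ALT of 5×ULN or more as a stopping criterion and attaches 24-hour Sponsor reporting and a liver event eCRF to events that require discontinuation. It asks for Medical Monitor notification for ALT from 3× to below 5×ULN without symptoms, and it requires SAE reporting of ALT at 3×ULN or more with raised, mainly direct bilirubin or raised INR. Clinically significant laboratory changes are recorded as AEs (section 7.2.8). AEs, SAEs and AEs leading to discontinuation are tabulated and carry the primary endpoint. A DMC reviews unblinded safety data (section 8.9). Being invisible in one table is not being undetected.

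It can also be said that ULN-multiple bands are table-shell detail the SAP may supply, and that nobody knows how many subjects will start above ULN.

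All of this stands as regards detection. It does not supply the missing summary. AE recording of a laboratory change rests on the Investigator's judgement of clinical significance. An isolated ALT of 5×ULN is an SAE only if it otherwise qualifies. Section 8.6 plans no tabulation of the liver event eCRF. Appendix 7's numerical transaminase criteria are for ALT, so an AST-led rise relies more on the laboratory tables. The SAP may add to section 8.6, but the protocol has already chosen the three categories and nothing supplied adds to them.

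**Conclusion.** The point holds as a weakness of tabulation. For subjects above ULN at Baseline the planned shift table cannot register worsening of any size. For the rest it cannot separate a small rise from a large one. What is lost is the between-arm count by size of rise, tied to each subject's starting value, for the only important identified risk and for an endpoint that names magnitude.

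It is not a failure of case detection or of subject protection. The classification result rests on the entry limit and the three categories alone. The number of subjects affected from a raised baseline rests on an assumed share, and it applies only to those still above ULN at Baseline, since criterion 7 is an eligibility limit. The change should be made before the SAP is signed.

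**What to change.** Keep the planned shift table. Add to section 8.6, and carry into the SAP, a table by treatment group for ALT, AST, ALP and total bilirubin that sets Baseline against the worst post-baseline value, with unscheduled repeat tests included. Use these bands:

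- ALT, AST and ALP: ≤1, >1–2, >2–<3, 3–<5 and ≥5×ULN.
- Total bilirubin: ≤1, >1–<2 and ≥2×ULN.

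Add a listing of subjects with ALT ≥3×ULN and bilirubin ≥2×ULN.

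The cut at 2×ULN matters: it matches the entry limit, and a single band from above 1× to below 3×ULN would still hide a rise from 1.2× to 2.9×ULN. The 3×, 5× and bilirubin 2× cuts are thresholds already in Appendix 7. The 3× and 5× cuts are set there for ALT, and using them for AST and ALP is for tabulation only. No clinical rule changes.

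The cost is a little table programming on data already collected. With about 10 subjects per arm many cells will be sparse, and a rise within one band, such as 1.2× to 1.5×ULN, will still not show.

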(Hamilton, 2020). Unlike trials of TNF-targeting agents, no increase in TB has been observed, despite GM-CSF's role in granuloma formation and TB protection in mice (Bryson, 2019; Hamilton, 2020). This benign safety profile has been corroborated in recently reported (not yet peer reviewed) trials of anti-GM-CSF mAbs for severe hospitalized COVID-19 subjects who were expected to be particularly susceptible to opportunistic infection (Patel, 2021; Temesgen, 2020). One suspected unexpected serious adverse reaction of bacterial pneumonia was reported in the COVID-19 Investigator-initiated study (CATALYST).

Another potential risk is the possibility of decreased neutrophil count/mild neutropenia. In the first-in-human (FIH) (M1-1188-001-EM) single dose escalation study of namilumab in healthy subjects (0.2 mg/kg to 8 mg/kg IV), a spontaneously reversible trend in decreased white blood cell (WBC) and absolute neutrophil count was observed in some subjects dosed with namilumab. The decrease in WBC was not clinically significant, and there was no dose-dependent pattern. Two subjects had clinically significant low neutrophil values during the trial: 1 subject on 0.5 mg/kg namilumab had a neutrophil count of  $1.0 \times 10^9/L$  on Day 8 and recovered without treatment by Day 15, and another subject on 3 mg/kg namilumab had a neutrophil count of  $1.1 \times 10^9/L$  on Day 29 and recovered spontaneously 4 days later. Both subjects recovered spontaneously without medical intervention. In the NEXUS study, neutrophil count, and WBC count decrease were recorded as drug related for 1 subject in the namilumab 80 mg treatment group and 1 subject in the namilumab 150 mg treatment group.

Neutralization of GM-CSF potentially may cause infection by depression of neutrophil and macrophage functions. The incidence of any severe and/or serious infection (with or without neutropenia) will be subject to ongoing pharmacovigilance (PV) monitoring in the clinical trial. To date, no serious adverse events (SAEs) of decreased neutrophil count and neutropenia have been reported with namilumab.

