#### **7.2.8. Clinical Safety Laboratory Assessments**

See [Appendix 5](#) for the list of clinical laboratory tests to be performed for Screening and safety monitoring; see the SOA ([Appendix 1](#)) for the timing and frequency.

The Investigator must review the laboratory report, document this review, and record any clinically significant changes occurring during the study as an AE. The laboratory reports must be filed with the source documents. New York State investigators will be blinded to the screening anti-GM-CSF auto-antibody laboratory results due to New York State regulations. These results will be made available to the New York State sites at the end of the trial.

Abnormal laboratory findings associated with the underlying disease are not considered clinically significant unless judged by the Investigator to be more severe than expected for the participant's condition.

All laboratory tests with values considered clinically significantly abnormal during participation in the study or within approximately 4 weeks after the last dose of study drug should be repeated until the values return to normal or Baseline or are no longer considered clinically significant by the Investigator or Medical Monitor.

If clinically significant values do not return to normal/Baseline within a period of time judged reasonable by the Investigator, the etiology should be identified, and the Sponsor notified.

All protocol-required laboratory tests must be conducted in accordance with the laboratory manual and the SOA ([Appendix 1](#)).

If laboratory values from non-protocol-specified laboratory tests performed at the institution's local laboratory require a change in participant management or are considered clinically significant by the Investigator (e.g., SAE or AE or dose interruption/discontinuation), then the results must be recorded.

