### **8.1. Determination of Sample Size**

The sample size for this study is not based on formal statistical calculations of study power. The planned sample size is considered sufficient to meet the primary objective.

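### Section 8.6 summarises laboratory results by visit only, which does not give the per-subject incidence and size of abnormalities that section 2.2 names as a secondary safety endpoint

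*Combined protocol and SAP*

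**What the plan says.** Section 2.2 lists as a secondary safety endpoint: "Incidence and magnitude of treatment-emergent laboratory abnormalities".

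Section 8.6 describes the laboratory analysis in three parts:
- Continuous summary: "Laboratory test variables will be summarized by treatment group and visit using descriptive statistics (number of subjects, mean, SD, minimum, maximum".
- Categorical summary: "Shift tables (low, normal, high) between Baseline and post-baseline timepoints will be presented by laboratory test and treatment" group.
- Other tests: "Data obtained from laboratory tests not required by the protocol will not be summarized but will be listed".

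It does not say what counts as a treatment-emergent laboratory abnormality and sets no threshold or grade. It has no row for a subject's worst value or for an abnormality at any time. For adverse events, by contrast, the same section says that a subject with repeated episodes is counted once.

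Several other passages generate results away from the scheduled visits:
- Section 7.2.8 asks for clinically significant abnormal tests to be repeated until they settle.
- Section 7.2.8 also covers local testing. Its rule begins "If laboratory values from non-protocol-specified laboratory tests performed at the institution's local laboratory require a change in participant management", extends to results that the Investigator considers clinically significant, and requires these to be recorded.
- Section 7.2.11 allows repeat or unscheduled samples for safety.
- Appendix 7 asks for liver tests to be repeated within 24 hours or within 24 to 72 hours, depending on the criterion met, and then monitored twice weekly or weekly.

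Section 8.6 closes by deferring: "Full details will be described in the Statistical Analysis Plan".

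**The concern.** The endpoint has two parts, and the planned tables deliver neither fully.

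Incidence is a count of subjects. A series of visit-by-visit tables does not say whether the abnormal subject at one visit is the same person as at the next, so the number ever abnormal cannot be read from it.

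Magnitude is shown only as the arm's minimum and maximum at each visit. A low/normal/high category cannot separate a value just above normal from the ALT multiples of 3 and 5 times the upper limit on which Appendix 7 acts.

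Results obtained between visits have no row at all. This matters most for the two laboratory risks that section 1.3 singles out: AST/ALT elevation (important identified risk) and decreased neutrophils (important potential risk). Safety is the primary objective and arms have 10 subjects, so one uncounted subject is 10 percentage points of incidence.

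**Working it through.** **Plan's own figures.** There is no power calculation to reproduce ("The sample size for this study is not based on formal statistical calculations of study power"). The one relevant stated figure is the 11 clinical laboratory collections in Table 6. Haematology and chemistry in Appendix 1 fall at Screening and on Days 1, 15, 43, 71, 99, 127, 155, 183, 211 and 238, which is 11 collections, so the figure reproduces. Nine are post-baseline. The gaps from Day 1 are 14 days, then seven of 28 days, then 27 days.

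**What by-visit counts can say about incidence.** Let c(v) be the number of subjects abnormal at visit v in an arm of 10, all normal at baseline. The number ever abnormal, N, is bounded by

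max c(v) ≤ N ≤ min(10, sum of c(v)).

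- One abnormal subject at each of three visits: max = 1 and sum = 3. The same tables fit 1/10 = 10% (one subject, three times) and 3/10 = 30% (three subjects, once each).
- One abnormal subject at each of the nine post-baseline visits: max = 1 and sum = 9. The same tables fit anything from 10% to 90%.

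These are constructed cases, not forecasts. They show that the planned tables do not determine the incidence, even when every value was measured at a scheduled visit.

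**Where off-schedule results go.** Under weekly liver monitoring, a 28-day gap holds 28/7 = 4 weekly tests. One coincides with the next scheduled visit and 3 fall between visits. A by-visit table has no row for those 3. A repeat normally follows an abnormal result that has already been measured. Leaving repeats out therefore mainly affects magnitude (the peak and the category reached). Leaving out an unscheduled sample that first detects an abnormality affects incidence.

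**The neutrophil example in section 1.3.** In the first-in-human study one low count was seen on Day 8 and had recovered by Day 15. Another was seen "on Day 29 and recovered spontaneously 4 days later", that is, by about Day 33. On this trial's calendar neither interval contains a nominal sample (Days 15 and 43). The ±3-day window would let an early Week 2 visit, on Days 12 to 14, catch the first. Measured from the latest dose, a sample taken before a 4-weekly dose falls on about Day 29, so a fall timed like the second could be sampled after a later dose.

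**Size of the undercount.** It depends on how many abnormalities are first found, or reach their peak, at unscheduled tests. The documents give no such rate, so it cannot be computed.

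**The case against.** **A stronger reading that the documents do not support.** A reader might infer that section 8.6 causes most short-lived abnormalities to be lost. If onset is uniform over the 237 days from Day 1 to Day 238, the chance that an episode of d days includes one of the nine post-baseline samples is 9d/237. That is 15% for 4 days, 27% for 7 days and 53% for 14 days, which suggests that 73% to 85% of 4- to 7-day episodes are missed. This figure should not be used. It describes the spacing of visits, not the listing rule, and a fall that nobody samples is missing under any analysis. The durations are not document data either: section 1.3 gives detection to recovery, not onset. Nor do the documents say that such falls would be found at a hospital test; both first-in-human subjects recovered without intervention.

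**Arguments that stand in part.**
- An abnormality present at a scheduled visit does enter that visit's shift table and its minimum or maximum. The gap is the subject-level count and the off-schedule results.
- Section 7.2.8 separates protocol-required tests from local tests outside the protocol. Repeats that the protocol calls for are arguably required tests and so not confined to listings. Section 8.6 does not settle this, and it gives no rule for placing repeats in a by-visit table.
- Clinically significant changes are recorded as adverse events and counted once per subject. That depends on Investigator judgement, and section 7.2.8 discounts findings attributed to the underlying disease unless they are worse than expected. The endpoint is laboratory abnormalities, not adverse events.
- Local results pass through much the same judgement before they are recorded, and they mix laboratories. This is a good reason to keep them out of the main table.
- Decreased neutrophils are an important potential risk, not an established effect. The first-in-human timing comes from two healthy subjects given single intravenous doses, with no dose-dependent pattern.
- Detail is left to the SAP, and no separate SAP text is in the documents, so a worst-value table cannot be ruled out. Nothing supplied provides one.

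**Conclusion.** The point holds in a limited form. Followed as written, section 8.6 does not yield the laboratory endpoint of section 2.2, because it has no abnormality definition, no once-per-subject count and no stated place for off-schedule results. That rests on the wording and on simple counting: tables showing at most 10% at any visit are compatible with 30% of subjects abnormal at some time. It needs no assumption about how long abnormalities last.

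The documents do not support a claim that abnormalities disappear from the trial. They remain in listings, and those judged clinically significant reach the adverse event tables. Nor do they support any figure for the share missed. This is an inexpensive improvement to the analysis of a safety endpoint, not a flaw in the safety monitoring.

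**What to change.** In section 8.6 or the SAP, before database lock:

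1. Define a treatment-emergent laboratory abnormality as a category that is new or worse than at baseline after the first dose.
2. Add a table of each subject's worst post-baseline value and category over all scheduled, repeat and unscheduled results of protocol analytes, counting each subject once. Show it by treatment within Cohort A, for Cohort B, and pooled as section 8.6 already plans. Cover at least neutrophils, ALT, AST and bilirubin.
3. For tabulation only, use the multiples in Appendix 7: ALT at 3 and 5 times the upper limit of normal, bilirubin at 2 times, and the two together. The Appendix 7 stopping table sets no AST multiple and no neutrophil level, so the SAP has to name those cut-points.
4. State that repeats called for by the protocol count as required tests.
5. Keep the by-visit means on scheduled central results. Show recorded local results only in a supportive version, classified against the reporting laboratory's own reference range.

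The change needs no extra visits or blood draws. It costs SAP wording, a few more tables, and local reference ranges for local results already recorded. The drawback is that subjects already abnormal are tested more often, so their worst value is drawn from more results. Giving the number of results per subject beside the table would let readers judge this.
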